Study 1: Exploratory study - identifying the benefits of pMDI versus Diskus for delivering fluticasone/salmeterol combination therapy in patients with chronic obstructive pulmonary disease (COPD)

Version Date: 7 February 2014

Protocol

**Study 1: Exploratory study -
identifying the benefits of pMDI
versus Diskus for delivering
fluticasone/salmeterol combination
therapy in patients with chronic
obstructive pulmonary disease
(COPD)**

To characterise patients with COPD initiating with fluticasone/salmeterol combination therapy via pMDI and Diskus and to identify and compare the potential benefits of using either device in the delivery of fluticasone/salmeterol combination therapy

Contents

OBJECTIVES	3
BACKGROUND	3
DATASOURCE	4
STUDY DESIGN	4
STUDY OUTCOMES	7
STATISTICAL ANALYSIS.....	8
TIMELINE, DELIVERY AND COSTINGS	9
RESEARCH TEAM	9
REFERENCES.....	9

OBJECTIVES

The aims of this exploratory study are to characterise patients with chronic obstructive pulmonary diseaseⁱ (COPD) initiating with fluticasone/salmeterol combination therapy delivered via pressurised metered dose inhaler (pMDI; also known as Evohaler) or Diskus (also known as Accuhaler); and to identify and compare the potential benefits of using either device in the delivery of fluticasone/salmeterol combination therapy.

This will be carried out by:

- (1) Characterising patients with COPD on fluticasone/salmeterol combination therapy via pMDI and Diskus.
- (2) Identifying and comparing the potential benefits of using pMDI versus Diskus in the delivery of fluticasone/salmeterol combination therapy in terms of both efficacy and adverse events, in particular:
 - a. Number of COPD exacerbations
 - b. Development of pneumonia infections
 - c. Type II diabetes diagnosis
 - d. Therapeutic indexⁱⁱ
 - e. Number of severe COPD-related events, including:
 - i. Lower respiratory tract infections
 - ii. Oral thrush

These are more clearly defined under 'Dataset Variables' below.

BACKGROUND

Inhaled corticosteroid use by patients with obstructive lung disease is associated with increased risk of pneumonia [1], increased risk of developing type-II diabetes [2] and increased risk of oral thrush [3].

Pressurised metred dose inhaler (pMDI) and Diskus devices both deliver fluticasone/salmeterol combination therapy, but the Diskus formulation includes added lactose. A previous Research in Real Life study [4] demonstrated that asthma patients on combination therapy via pMDI have significantly greater odds of achieving asthma control and fewer exacerbations than those on dry powder inhalers such as Diskus.

This study aims to explore and identify the benefits of using either pMDI versus Diskus for delivering fluticasone/salmeterol combination therapy in patients with COPD.

This study will focus on patients with COPD initiating with Seretide[®] combination therapy, delivered via

- pMDI (also known as Evohaler)
- Diskus (also known as Accuhaler)

In addition, the number of patients in the following sub-populations will be reported:

ⁱ COPD is defined as a common, preventable and treatable disease characterised by persistent airflow limitation that is usually progressive and associated with an enhanced chronic inflammatory response in the airways and lungs to noxious particles and gases.

ⁱⁱ Therapeutic index = highest dose not causing harm (side effect) / lowest dose that causes benefit (reduced number of severe COPD-related events).

- COPD without asthma
- COPD with asthma
- COPD +/- asthma AND eosinophils $>0.4 \times 10^9/L$

DATASOURCE

This study will use the Optimum Patient Care Research Database (OPCRD), which comprises anonymous data extracted from primary care practices in order to perform reviews of their chronic respiratory services. Two types of anonymised patient data are typically collected:

- (1) Routine clinical data
 - OPC software interfaces with primary care practice management systems and extracts disease coding and prescribing information.
- (2) Questionnaires
 - Patients identified as recipients of the respiratory service under review are invited to complete validated disease assessment questionnaires to better understand their current health status (and/or possible reasons for sub-optimal status).
 - Anonymised questionnaires are assigned a unique code to aid matching routine data to questionnaire results.

The OPCRD has been approved by Trent Multi Centre Research Ethics Committee for clinical research use. The anonymous, longitudinal patient data offers a high-quality data source for use in clinical, epidemiological and pharmaceutical research. It enables research to be carried out across a broad range of respiratory areas.

STUDY DESIGN

The study will be a retrospective database analysis, consisting of a (one year) baseline period, a (one year) outcome period and an index date, defined as the date of the first prescription for Seretide[®] combination therapy at which patients with evidence of COPDⁱⁱⁱ will be split into the following groups:

- (1) Those using pMDI (also known as Evohaler)
- (2) Those using Diskus (also known as Accuhaler)

The baseline period will be one year prior to and including the index date^{iv} and it will be used for patient characterisation, such as demographics, baseline therapy, disease severity and number of COPD exacerbations. The outcome period will be one year following the index date, and the effect of device on COPD-related severe exacerbations, adverse events and therapeutic index will be investigated.

ⁱⁱⁱ COPD diagnostic code (at any time) and recorded spirometry data supporting COPD diagnosis within 5 years window of diagnosis code. Note that individuals with asthma and bronchiectasis will not be excluded.

^{iv} except for therapy prescribed at IPD (which is included in the outcome).

[figure not shown]

Figure 1: Study design

Inclusion Criteria

In order to be included in the study, patients must fit the following criteria:

- (1) COPD diagnosis (COPD diagnostic code (at any time) and COPD confirmed by FEV/FVC ratio <0.7 ever in medical history. Note that individuals with asthma and bronchiectasis will not be excluded)
- (2) Two years of continuous practice data comprising 1 year baseline data and 1 year outcome data
- (3) ≥2 prescriptions for Seretide® pMDI OR Seretide® Diskus during 1 year outcome period, inclusive of IPD (i.e. 1 Seretide® prescription at IPD plus ≥1 prescriptions for the same device during 1 year outcome period).
- (4) Age ≥35 at time of initiating with Seretide

Exclusion Criteria

- (1) Evidence of restrictive lung disease other than bronchiectasis (diagnostic code)
- (2) ≥1 prescription for inhaled corticosteroids (ICS), including as part of a fixed dose combination, during baseline period (excluding IPD)
- (3) Evidence of pneumonia during baseline period (diagnostic code)
- (4) No maintenance oral steroids in baseline

Dataset Variables

Demographics (gender, age, weight, height, BMI, smoking status, disease severity (FEV1 percent predicted, FEV1/FVC ratio, GOLD group, mMRC score)) will be calculated at (or closest to) the IPD. Disease severity will be regarded as missing if >5 years either side of IPD.

Treatment therapy will be recorded in the year prior to the IPD.

Baseline blood eosinophil counts will be recorded^v (where valid is defined as a numeric value expressed /L).

Co-morbidities will be examined regardless of when diagnosis relative to the index date was made and include:

- Ischaemic heart disease
- Heart failure diagnosis
- Diabetes diagnosis
- Asthma diagnosis
- Bronchiectasis diagnosis
- Rhinitis
- Eczema
- Osteoporosis diagnosis
- Gastroesophageal reflux disease (GERD)
- Anxiety/depression diagnosis
- Chronic kidney disease
- Hypertension

Note that all of the above co-morbidities (except diabetes) are identified by GP diagnostic read code, ever recorded. Diabetes is identified by GP anti-diabetic drug prescriptions; AND/OR by GP diagnostic read code, ever recorded.

For the baseline and outcome periods, the following will be calculated:

- COPD exacerbations^{vi} and the date of event (each component of the definition will also be analysed separately)

^v closest value to IPD (missing if >5 years either side of IPD).

^{vi} Where an exacerbation is defined as an occurrence* of:

- COPD-related: Unscheduled hospital admission / A&E attendance^{**}; OR
- An acute course of oral steroids prescribed with evidence of a respiratory review^{***}; OR
- Antibiotics prescribed with evidence of a respiratory review^{***}.

*Where ≥ 1 oral steroid course / hospitalisation / antibiotics prescription occur within 2 weeks of each other, these events will be considered to be the result of the same exacerbation (and will only be counted once).

****COPD-related Hospitalisations:** consist of either a definite COPD Emergency Attendance or a definite COPD Hospital Admission; OR a generic hospitalisation read code which has been recorded on the same day as a **Lower Respiratory Consultation**[§] (see below - excluding where the only lower respiratory code recorded on that day was for a lung function test).

*****Evidence of a Respiratory Review** - consists of the following:

- a) Any **Lower Respiratory Consultation**[§] (see below) and
- b) Any additional respiratory examinations, referrals, chest x-rays, or events.

§ Lower Respiratory Consultations - consist of the following:

- a) Lower Respiratory read codes (including Asthma, COPD and LRTI read codes);

- Development of pneumonia (recorded as absence/presence of, and confirmed via: chest X-ray within a month of a pneumonia diagnosis OR hospitalisation within a month of a pneumonia diagnosis). Note that baseline values will be zero due to study exclusion criteria.
- Development/progression of diabetes
 - Development of diabetes (recorded as absence or presence of) during outcome period for patients (for patients without diabetes at or prior to IPD)
 - Progression of ongoing type-II diabetes treatment to insulin (defined as no insulin prescription during 1 year baseline period AND any insulin prescriptions during 1 year outcome period)
 - Diabetic control (defined as change in HbA1c value prior to starting Seretide® and after IPD)
 - Diabetic medication (defined as change in anti-type-II diabetic medication dosage OR medication type)
- Number of potential severe COPD-related adverse events and date of event including
 - Oral thrush
 - Lower respiratory tract infections
 - Bronchitis
 - Dysphonia / hoarseness
 - Nasopharyngitis (common cold)
 - Sinusitis
 - Hypokalemia (low blood potassium)
 - Muscle or joint pain
- ICS dose (in outcome period only) and date of ICS prescription

Matching will be used if required.

STUDY OUTCOMES

The primary aim of the current study is to identify baseline and outcome characteristics of patients with COPD initiating with Seretide® combination therapy via pMDI and Diskus and to identify and compare the potential benefits of using each device in the delivery of Seretide®. Among other events, the effect of device on the following outcomes will be investigated:

(1) COPD related severe exacerbations

Where an exacerbation is defined as an occurrence^{vii} of:

- COPD-related: Unscheduled hospital admission / A&E attendance^{viii}; OR
- An acute course of oral steroids prescribed with evidence of a respiratory review^{ix};
OR

-
- b) Asthma/COPD review codes excl. any monitoring letter codes;
 - c) Lung function and/or asthma monitoring.

^{vii}Where ≥ 1 oral steroid course / hospitalisation / antibiotics prescription occur within 2 weeks of each other, these events will be considered to be the result of the same exacerbation (and will only be counted once).

^{viii}**COPD-related Hospitalisations:** consist of either a definite COPD Emergency Attendance or a definite COPD Hospital Admission; OR a generic hospitalisation read code which has been recorded on the same day as a **Lower Respiratory Consultation*** (see below - excluding where the only lower respiratory code recorded on that day was for a lung function test).

^{ix}**Evidence of a Respiratory Review** - consists of the following:

- Antibiotics prescribed with evidence of a respiratory review^{ix}.

(2) COPD related adverse events

Where adverse events include the number of incidences of:

- Oral thrush
- Lower respiratory tract infections
- Bronchitis
- Dysphonia / hoarseness
- Nasopharyngitis (common cold)
- Sinusitis
- Hypokalemia (low blood potassium)
- Muscle or joint pain

(3) Therapeutic index

Therapeutic index = highest dose not causing harm (side effect) / lowest dose that causes benefit (reduced number of severe COPD-related events).

For the highest dose not causing harm: the median dose at which no (any) adverse events occur

For the lowest dose that causes benefit (reduced number of severe COPD-related events): median dose at which patients show no increase in number of exacerbations in outcome

STATISTICAL ANALYSIS

Statistically significant results will be defined as $p < 0.05$ and trends as $0.05 \leq p < 0.10$

Summary statistics will be produced for all baseline and outcome variables, as a complete dataset and by device. For variables measured on the interval or ratio scale, these will include:

Sample size (n) & percentage non-missing

Mean & Variance / Standard Deviation

Range (Minimum / Maximum)

Median & Inter-quartile Range (25th and 75th percentiles)

For categorical variables, the summary statistics will include:

Sample size (n)

Range (if applicable)

Count and Percentage by category (distribution)

Treatment arms will be compared using t-test / Mann Whitney U-test (depending on distribution) for variables measured on the interval/ratio scale and using a chi square test for categorical variables.

a) Any **Lower Respiratory Consultation*** (see below) and

b) Any additional respiratory examinations, referrals, chest x-rays, or events.

* **Lower Respiratory Consultations** - consist of the following:

a) Lower Respiratory read codes (including Asthma, COPD and LRTI read codes);

b) Asthma/COPD review codes excl. any monitoring letter codes;

c) Lung function and/or asthma monitoring.

TIMELINE, DELIVERY AND COSTINGS

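### The stated device comparisons have no practice term, so if device choice and outcome recording both vary by practice, recording differences can pass for device effects and the 5% error rate is exceeded.

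*Protocol*

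**What the plan says.** The analysis choice at issue is in STATISTICAL ANALYSIS: "Treatment arms will be compared using t-test / Mann Whitney U-test (depending on distribution) for variables measured on the interval/ratio scale". Categorical variables get a chi-square test. Results below 0.05 are called significant, and those from 0.05 up to 0.10 are called trends.

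The rest of the protocol gives the setting:

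- DATASOURCE describes a database "which comprises anonymous data extracted from primary care practices" and adds that "OPC software interfaces with primary care practice management systems and extracts disease coding and prescribing information". The practice system is therefore the source of the prescription that sets the device group and of the coded clinical events.
- STUDY OUTCOMES and the exacerbation footnotes: one route to an exacerbation is "An acute course of oral steroids prescribed with evidence of a respiratory review", and antibiotics follow the same rule. Part of what makes up a respiratory review is "Any additional respiratory examinations, referrals, chest x-rays, or events". A generic hospitalisation code counts only if a lower respiratory consultation was recorded that day.
- Dataset Variables: a pneumonia diagnosis needs a chest X-ray or a hospitalisation within a month to be confirmed.
- Dataset Variables also lists what is carried for each patient, beginning "Demographics (gender, age, weight, height, BMI, smoking status, disease severity (FEV1 percent predicted, FEV1/FVC ratio, GOLD group, mMRC score)) will be calculated" and going on to treatment, eosinophils, co-morbidities and events. All of these are patient-level. Practice appears only in the inclusion criterion on continuous data.
- The only mention of confounding control is that matching will be applied if it proves necessary. No matching variables or trigger are given.

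**The concern.** A t-test, Mann-Whitney or chi-square test on two device groups assumes independent patients and adjusts for nothing. Patients here are grouped in practices, and many outcomes exist only if the practice examined, referred, ordered an X-ray or made an entry. Two separate harms could follow if practices differ both in which device they tend to prescribe and in how fully they record.

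- **Bias.** If practices that record more lean towards one device, that device shows more exacerbations and adverse events with no true difference. A larger sample makes the false finding more likely.
- **Error rate.** Even if practice recording and device preference are aligned only by chance, patients who share a practice tend to share both device and recording level. The naive standard error is then too small, and the 0.05 and trend thresholds are looser than they look.

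The results would be read as benefits or harms of a device, so both matter for interpretation.

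**Working it through.** The protocol text gives no sample size, number of practices, patients per practice or ICC, so there is no planned figure to reproduce. Everything below is an illustration on stated assumptions.

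**Inputs.** From the protocol: significance at 0.05 (taken as two-sided, since sidedness is not stated) and unadjusted two-group tests. Assumed: m patients per practice, an outcome ICC, and a device ICC. The device ICC is the extent to which patients of one practice share a device: 0 means unrelated to practice, 1 means one device per practice.

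**Error rate.** Variance inflation of the naive comparison is

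VIF = 1 + (m − 1) × ICC_device × ICC_outcome,

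and the actual error of a nominal 5% test is 2 × [1 − Φ(1.96 / √VIF)]. With m = 20:

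| Device ICC | Outcome ICC | VIF | Standard error understated by | Actual error |
|---|---|---|---|---|
| 0.2 | 0.02 | 1 + 19 × 0.004 = 1.076 | 1.04 | 0.059 |
| 0.5 | 0.02 | 1 + 19 × 0.010 = 1.19 | 1.09 | 0.072 |
| 0.5 | 0.05 | 1 + 19 × 0.025 = 1.475 | 1.21 | 0.107 |
| 1 | 0.02 | 1 + 19 × 0.020 = 1.38 | 1.17 | 0.095 |
| 1 | 0.05 | 1 + 19 × 0.050 = 1.95 | 1.40 | 0.160 |

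The range is therefore about 6% to 16%.

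**Where there is no inflation.** If device choice is unrelated to practice (device ICC 0), VIF = 1 and the error is 0.050. If devices are exactly balanced within each practice, VIF = 1 − ICC_outcome. The error is then 0.044 at outcome ICC 0.05 and 0.039 at 0.10, slightly conservative.

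**How wide the range could be.** With one device per practice, m = 5 and outcome ICC 0.01 give VIF 1.04 and error 0.055. With m = 50 and outcome ICC 0.10, VIF is 5.9 and the error 0.42.

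**Simulation check.** T-tests on 50 practices of 20 patients, outcome ICC 0.05, no device effect, 4000 runs: rejection rates were 0.044, 0.083, 0.118 and 0.160 at device ICC 0, 0.3, 0.6 and 1. The formula gives 0.050, 0.084, 0.118 and 0.160.

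**Bias.** Suppose there is no device effect, high-recording practices record an event in 25% of patients and low-recording practices in 15%, and 60% of pMDI but 40% of Diskus patients are in high-recording practices. The recorded rates are

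- pMDI: 0.6 × 25% + 0.4 × 15% = 21%
- Diskus: 0.4 × 25% + 0.6 × 15% = 19%

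The test then gives p < 0.05 with probability about 0.12 at 500 per group and 0.35 at 2000 per group. With a 70/30 split (22% against 18%) the probabilities are 0.35 and 0.89.

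**The case against.** The strongest objection is that the premise is not in the document. The protocol says that prescribing data come from practice systems. It does not say what decides the device or that practices differ in preference. This stands: a reader might infer that practices choose the device and that the p-values are therefore too small, but the documents support neither as fact. Inflation needs both device and outcome to cluster by practice.

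A reader might also infer that every outcome rests on practice coding. That is too broad. Insulin, diabetic medication and ICS dose come from prescriptions, and HbA1c is a measured value. The protocol does not say how thrush, hoarseness and the other listed adverse events are identified; its Read-code sentence covers co-morbidities. The same-day consultation rule applies only to generic hospitalisation codes.

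Third, a stable recording difference would also appear in the baseline year. Exacerbations and adverse events are counted in both periods and summarised by device, and the benefit part of the therapeutic index compares outcome with baseline. Matching on baseline counts would remove part of the difference. This is right, so it would be too strong to say that matching cannot help. But the protocol does not commit to matching on those counts, and the stated tests do not adjust for them.

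Fourth, random intercepts and robust errors are often left to an SAP, a practice identifier may exist as a data key, and the study is exploratory. These points limit the weight of the finding. They do not remove it, because the protocol itself names the tests and applies significance rules to the effect of device.

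**Conclusion.** The point holds conditionally. The tests named in STATISTICAL ANALYSIS ignore practice, in data where practice systems supply both the device prescription and most of the records behind the outcomes. If practices differ in device preference and also in recording or referral habits, device and recording are confounded and the 5% error is exceeded: about 6% to 16% with 20 patients per practice, device ICC 0.2 to 1 and outcome ICC 0.02 to 0.05. All of these figures are assumptions. If device choice does not depend on practice, the tests keep their level. The actual size cannot be worked out from the protocol, and it cannot be checked in the data unless practice is retained. This is a cheap improvement to a stated method; it does not show that the planned results would be wrong.

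**What to change.** - Name the anonymised practice identifier in Dataset Variables and retain it in the analysis dataset.
- In STATISTICAL ANALYSIS, make each device comparison of an outcome with a model suited to that outcome, using either a practice random intercept or cluster-robust standard errors. The tests now named can stay for describing baseline.
- Add a within-practice comparison (practice as stratum or fixed effect) as a sensitivity check. It is needed as well because robust errors correct the precision but leave a biased estimate where it is. If the within-practice and overall estimates disagree, interpret the device effect with caution.

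The cost is a change of analysis wording. Data are extracted from practice systems, so no new collection should be needed. The downside is slightly wider intervals, and practices that use only one device drop out of the within-practice check.

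### Footnote iv moves all index-date therapy into the outcome, so a steroid or antibiotic course issued at the initiating visit can be scored as an outcome exacerbation

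*Protocol*

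**What the plan says.** Three parts of the protocol bear on this.

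- **Periods (Study Design).** "The baseline period will be one year prior to and including the index date". The protocol then lists what this period serves to describe, "such as demographics, baseline therapy, disease severity and number of COPD exacerbations". For follow-up it sets a second window: "The outcome period will be one year following the index date".
- **Exception (Study Design, footnote iv, attached to the baseline definition).** "except for therapy prescribed at IPD (which is included in the outcome". The footnote does not say which therapy it means.
- **Exacerbation definition (Dataset Variables, footnote vi, repeated under Study Outcomes).** An exacerbation is any of three things. The hospital component is "COPD-related: Unscheduled hospital admission / A&E attendance". The steroid component is "An acute course of oral steroids prescribed with evidence of a respiratory review". The antibiotic component is "Antibiotics prescribed with evidence of a respiratory review". The last two are dated by a prescription.

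Exacerbations are the first listed outcome. They also feed the therapeutic index, whose denominator is the median dose among patients whose exacerbation count does not rise from baseline to outcome.

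**The concern.** Read as written, footnote iv covers every prescription issued on the index date, including an acute oral steroid or antibiotic course. Such a course then falls in the outcome period. A hospital or A&E event on the same day is not therapy and stays in baseline, as does the respiratory review that qualifies the prescription as an exacerbation. One illness on one day can be divided between the two periods.

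An event on the day the device is first prescribed cannot reflect the effect of that device. Three things are at stake:

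- If index-day courses are equally common with both devices, they add the same constant to both outcome rates and pull any real difference towards no difference.
- If they are more common with one device, they create or distort a difference. Matching on baseline exacerbations, which the protocol allows if required, would not see these courses, because the footnote has moved them out of baseline.
- For the therapeutic index, a patient whose only exacerbation is an index-day course would be recorded as 0 then 1 (an increase) instead of 1 then 0.

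**Working it through.** **Step 1: the two readings side by side.** The protocol states no exacerbation rate, event count or index-day share, so there is no figure of its own to reproduce. The check starts from the definitions.

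| Index-day record | Literal reading of footnote iv | Narrow reading (therapy = Seretide/ICS) |
|---|---|---|
| Seretide prescription | Outcome | Outcome |
| Acute oral steroid or antibiotic course | Outcome | Baseline |
| Respiratory review supporting that course | Baseline | Baseline |
| Hospital admission or A&E attendance | Baseline | Baseline |

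The readings differ only in the second row, which holds two of the three exacerbation components.

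**Step 2: effect on the rate ratio (all inputs assumed).** Let mu be the true post-index rate per year in the reference arm, RR the true rate ratio, and p1 and p0 the shares of patients with an index-day course in the comparison and reference arms. On the literal reading:

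observed ratio = (mu × RR + p1) / (mu + p0)

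With mu = 0.9:

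- p1 = p0 = 0.20, RR = 0.80: (0.72 + 0.20) / (0.90 + 0.20) = 0.92 / 1.10 = 0.836
- p1 = 0.30, p0 = 0.20, RR = 1.00: (0.90 + 0.30) / 1.10 = 1.091
- p1 = 0.30, p0 = 0.20, RR = 0.80: (0.72 + 0.30) / 1.10 = 0.927

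**Step 3: range.** Take mu from 0.5 to 1.5 and the index-day share from 5% to 30%.

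- Equal shares, true ratio 0.80: from (1.20 + 0.05) / 1.55 = 0.806 to (0.40 + 0.30) / 0.80 = 0.875.
- Share 5 to 10 points higher in the comparison arm, true ratio 1.00: from (1.50 + 0.35) / 1.80 = 1.028 to (0.50 + 0.15) / 0.55 = 1.182.

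The formula adds the whole share to the outcome count. The protocol merges courses within two weeks of each other: "these events will be considered to be the result of the same exacerbation (and will only be counted once". An index-day course followed by another within that window would therefore add no extra event, so these figures are nearer an upper limit for the inputs used.

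**Step 4: effect on the no-increase criterion.** Assume independent Poisson counts with the same rate in both periods, plus one index-day event. The probability that the outcome count exceeds the baseline count is:

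| Rate per year | Index-day event in outcome | Index-day event in baseline | No index-day event |
|---|---|---|---|
| 0.5 | 73.3% | 5.9% | 26.7% |
| 1.0 | 65.4% | 13.0% | 34.6% |
| 1.5 | 62.2% | 18.2% | 37.8% |

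Where the event is placed largely decides how such a patient is classified. The last column shows that neither placement is neutral.

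**The case against.** The strongest reply is that footnote iv was never meant to cover acute courses. The body text lists baseline therapy and number of exacerbations as separate uses of a period that includes the index date, and the footnote exempts only therapy. The outcome year is described as following the index date. The two eligibility criteria that treat the index date specially, inclusion 3 and exclusion 2, concern Seretide and ICS only. On that reading the index-day exacerbation is a baseline event and no bias arises. This is plausible, and it rules out saying that the protocol does score such events as outcomes. It does not remove the problem. The footnote is attached to the general period definition and names no drug, and the two readings score the same patient in opposite ways.

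Three further objections stand in part:

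- A reader might infer that the exacerbation which prompted treatment is routinely counted as a failure of the device. The protocol does not say why or when patients start Seretide, so how often an acute course falls on the index date is an assumption.
- The larger distortions need different shares by device, and the protocol gives no evidence of that.
- Which period owns an episode that straddles the index date under the two-week rule is derivation detail that may sit in an SAP that is not shown. It is not raised here as a defect.

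**Conclusion.** The point holds as a fault of wording with real consequences, not as proof of bias. As written, footnote iv allows an index-day steroid or antibiotic course to enter the first listed outcome and the therapeutic-index criterion. This sits against the body text, which uses a baseline that includes the index date to count exacerbations.

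The size depends entirely on assumed inputs. At 0.9 exacerbations a year and a 20% share in both arms, the effect is modest dilution, from 0.80 to 0.84. A difference of 30% against 20% would produce an apparent ratio of 1.09 where none exists. If the narrow reading is applied, both effects are zero. The study is exploratory, but the ambiguity reaches its first listed outcome and is almost free to remove, so it should be corrected.

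**What to change.** - Limit footnote iv to the Seretide/ICS prescription itself.
- State that acute oral steroid and antibiotic courses issued on the index date count in baseline, with the other index-day events.
- State that outcome exacerbations are counted from the day after the index date. This makes explicit what the body text already implies.

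The cost is one footnote and one date rule in the data query, with no patients lost. There is one downside. Fixing an index-day event in baseline brings some regression to the mean into before-after comparisons: in the illustration above, the chance of an increase falls to 6–18%, against 27–38% for a patient without such an event. This should be noted when the no-increase criterion is interpreted. The between-device comparison of outcome counts is not affected by it.

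### COPD eligibility is defined in two conflicting ways, and neither definition requires evidence of COPD by the index date

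*Protocol*

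**What the plan says.** Under Study Design, patients with COPD are divided by device at the index date, which is "defined as the date of the first prescription for Seretide". Footnote iii explains what counts as COPD at that step: "COPD diagnostic code (at any time) and recorded spirometry data supporting COPD diagnosis within 5 years window of diagnosis code".

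The Inclusion Criteria that follow are introduced as mandatory: "In order to be included in the study, patients must fit the following criteria". Criterion (1) then defines COPD again, as a diagnostic code at any time together with "COPD confirmed by FEV/FVC ratio <0.7 ever in medical history". Both texts add that asthma and bronchiectasis are not grounds for exclusion.

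On timing, "The outcome period will be one year following the index date", and Criterion (2) requires "Two years of continuous practice data comprising 1 year baseline data and 1 year outcome data".

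**The concern.** There are two separate faults.

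The first is a contradiction in the main eligibility criterion. Two programmers working from the same Protocol, one from the footnote and one from the criteria list, could extract different cohorts. Every summary and device comparison depends on who is in the cohort.

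The second is a design fault that both definitions share. The stated aim concerns COPD patients initiating fluticasone/salmeterol, yet neither definition requires the code or the spirometry to exist when therapy starts. Selecting on later information means that what happens during follow-up can affect who is eligible. The exacerbation definition gives a plausible route: steroid or antibiotic courses count only with a respiratory review, and that review can rest on COPD codes or lung-function monitoring. A patient who exacerbates in the outcome year may therefore be more likely to acquire the code or spirometry that admits them.

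**Working it through.** The Protocol gives no figure to reproduce, so the check sets the two rules side by side and applies them to hypothetical timelines.

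| Element | Footnote iii | Inclusion Criterion (1) |
|---|---|---|
| Diagnostic code | any time | any time |
| Spirometry | supports the diagnosis; no ratio stated | ratio below 0.7 |
| Window between spirometry and code | 5 years | none |
| Tied to index date | no | no |

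Set the index date at year 0, so that the outcome year runs from 0 to 1. Assume that each patient has no spirometry other than that listed and meets all other criteria.

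| Patient | Code | Spirometry | Gap | Footnote iii | Criterion (1) |
|---|---|---|---|---|---|
| A | year −1 | only ratio below 0.7 at year −8 | 8 − 1 = 7 years | out | in |
| B | year −1 | judged supportive at year −1, no ratio below 0.7 on record | 0 years | can be in | out |
| C | year +3 | first ratio below 0.7 at year +4 | 4 − 3 = 1 year | in | in |

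1. A and B together show that neither set contains the other. At least three cohorts are consistent with the text: Criterion (1) alone, footnote iii alone, or both required. The Protocol does not choose among them.
2. C passes both rules. The code comes 3 − 1 = 2 years after the outcome year ends, and the confirming ratio 4 − 1 = 3 years after. Choosing between the two rules, or requiring both, does not remove C.
3. Criterion (2) does not remove C either. It sets a minimum span of data and does not cut the record off at the end of the outcome year.
4. The footnote's window is measured from the code, and the code is itself free to fall at any time, so the window gives no indirect link to the index date.

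**The case against.** The strongest reply to the first fault is that the numbered criteria are mandatory and the footnote only explains a phrase in the design narrative, so the list should govern. The two texts can also be satisfied together, and they part only for patients like A and B, whose number is unknown. That is a reasonable reading, but the Protocol does not state it. The footnote is attached to the very step at which patients are assigned to device groups, so a programmer could equally treat it as operative.

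On timing, the reply is that use of post-index data looks deliberate. Co-morbidities are taken whenever they were diagnosed, and for severity the rule is "Disease severity will be regarded as missing if >5 years either side of IPD". COPD is described as persistent and usually progressive, so a later code may reflect disease already present. The ratio clause in Criterion (1) could also be read as history up to the index date. This makes post-index coding a design choice on which the two definitions agree, so it does not add to the ambiguity about who is in the cohort. It does not remove the fault: describing a patient with later data is different from admitting a patient because of later data. Even on the narrow reading of the ratio clause, the code is left open in both places.

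A reader might go further and infer that late-coded asthma patients would carry the asthma device effect cited in the Background into this study and by themselves produce a pMDI advantage. The Protocol does not support that. It gives no size for the earlier effect, whose comparator was dry powder inhalers as a class, and no share of such patients. COPD with asthma is an intended part of the population. The age limit of 35 and the exclusion of inhaled corticosteroids in the baseline year narrow the group further. If the share differed between devices, even the direction would not be fixed.

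**Conclusion.** Both faults stand, as two distinct points. The two COPD definitions conflict and nothing ranks them, so the cohort is not uniquely specified. Independently, both definitions admit patients whose first evidence of COPD comes after the outcome year, which conditions entry on post-index information and sits badly with the stated aim.

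The conflict follows from the wording alone. The timing point assumes only that the database holds records beyond the outcome year for some patients, which the Protocol does not rule out. The number of patients affected, and the direction and size of any bias, cannot be derived. The study is exploratory and the remedy is simple, so this is a correction that should be made before data extraction. It does not show that the device comparison will be wrong.

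**What to change.** Use one COPD definition, worded identically in footnote iii and Inclusion Criterion (1), that states the ratio threshold, the window around the code (including whether it runs in both directions) and the anchor date. For the main analysis:

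- a COPD code on or before the index date;
- an FEV1/FVC ratio below 0.70 on or before the index date;
- the two within 5 years of each other.

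Write the ratio as FEV1/FVC, as the Dataset Variables section already does. Run the unrestricted rule (code at any time, low ratio at any time) as a sensitivity analysis, and report by device how many patients enter under each rule, so that the effect of the choice can be seen.

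The cost is a change of wording in two places, a change to the extraction query and one additional analysis. The main cohort will lose some patients. The Protocol does not allow that loss to be estimated, and a count from the database before the definition is fixed would settle it.
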